#### 4. STATISTICAL ANALYSES

#### 4.1. General Considerations

### 4.1.1. General Methodology

Unless otherwise stated, the Safety Analysis Set be used for safety displays and the Full Analysis Set (FAS) will be used for all other displays. FAS-Modified and Safety-Modified analysis sets will be used for a selected number of displays as sensitivity analyses. FAS-China, FAS-Japan, Safety-China and Safety-Japan will be used for China and Japan specific outputs respectively. The Programming Specification document will provide more details.

Unless otherwise stated, all intercurrent events for primary, secondary, or other endpoints will be handled under the primary estimand strategy.

This SAP specifies the analytical approaches for the global submission requirements, unless otherwise specified. Further analytical considerations may be made for the regional displays (i.e. model convergence considerations) where appropriate.

The randomization is stratified based on occurrence of previous surgery for nasal polyps and unless otherwise stated, this variable will be included as a covariate in the statistical models. In the case of an incorrect stratification at the time of randomization, the actual stratum will be used rather than the randomized stratum.

Confidence intervals will use 95% confidence levels unless otherwise specified.

Unless otherwise specified, continuous data will be summarized using descriptive statistics: n, mean, standard deviation (std), median, minimum and maximum. Categorical data will be summarized as the number and percentage of participants in each category.

#### 4.1.2. Baseline Definition

For all visit-based endpoints, including the co-primary endpoint of endoscopic NP score, baseline will be defined as the latest non-missing measurement collected prior to the first dose of study treatment. This will generally be from the Day 1 (Visit 2) assessment but may be from an unscheduled or screening assessment. In the case a visit-based assessment was collected after the first dose of study treatment, but still on the day of the randomization visit on Day 1 (Visit 2), then that assessment may be used.

For daily efficacy endpoints collected in the eDiary, baseline will be the average score from the 28 calendar days up to and including the date of randomization. This means the average will be based on the non-missing data from Day -27 to Day 1 inclusive. There must be a minimum of 4 non-missing values from Day -6 to Day 1 inclusive in order to derive the baseline, otherwise it will be set to missing.

Unless otherwise stated, if baseline data is missing no derivation will be performed and baseline will be set to missing.

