In rare instances and following consultation with the Medical Monitor a participant can be rescreened. Rescreened participants are required to sign a new ICF.

At the end of the run-in period, study participants must fulfill the following additional criteria in order to be randomized to study treatment:

- Endoscopic bilateral NP score of at least 5 out of a maximum score of 8 (with a minimum score of 2 in each nasal cavity) taken at Visit 1 as assessed at central laboratory
- 2. Mean nasal obstruction VRS of 2 or greater over the last 7 days preceding Visit 2 (excluding Visit 2) (from electronic diary [eDiary])
- 3. eDiary compliance for at least 4 out of the last 7 days preceding Visit 2 (excluding Visit 2).
- 4. Not had any NP surgery between Visit 1 and Visit 2 and not on a waiting list for NP surgery at the time of randomization.
- 5. Laboratory abnormality: No evidence of clinically significant abnormality in the haematological, biochemical or urinalysis screen at Visit 1, as judged by the investigator.
- Liver Chemistry Tests: obtained at Visit 1:
 - $ALT \le 2x$ upper limit of normal (ULN)
 - Bilirubin ≤ 1.5 x ULN (isolated bilirubin ≥ 1.5 x ULN is acceptable if bilirubin is fractionated and direct bilirubin <35%)
- ECG: QTcF < 450 msec, or QTcF < 480 msec for participants with Bundle Branch Block, in the 12-lead ECG machine-read at Randomization Visit 2. No evidence of a clinically significant abnormality in the central over-read of the 12-lead ECG conducted at Screening Visit 1 that would impact the participant's participation during the study, based on the evaluation of the Investigator. See Section 8.3.3 for further ECG guidance.
- 8. **Asthma Exacerbation:** No asthma exacerbations during run-in period. An exacerbation is defined as worsening of asthma requiring the use of systemic corticosteroids for at least 3 days and/or overnight stay at emergency department visit, or hospitalization.

218079

- 9. **Maintenance Therapy:** No new systemic corticosteroids for CRSwNP have been started during the run-in period.
- 10. If the participant has an URTI or cold during run-in, then run-in should be extended to have the Visit 2, 2 weeks post the resolution of the cold but no greater than a total of 6 weeks from Visit 1. Participants with colds that are not resolved within the 4th week of the nominal run-in period (28 days after screening) will be ineligible for randomization as they would have exceeded the 6 weeks period.

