## 6.2.1. Study-Level (Overall) Compliance

The study-level (overall) compliance for all eCOA assessments collected in the study will be assessed for all participants at all time-points between baseline through to the date of the participant's study completion or withdrawal. If an eCOA is only assessed for a certain sub-population, the compliance for only that sub-population will be included in the compliance calculation (i.e. ACQ-5 only administered in participants with asthma). The list of eCOA assessments that comprise the study-level (overall) compliance include all eCOA assessments collected within the study: VRS, VAS, Nasal Obstruction VAS, SNOT-22, PGIS, PGIC, ACQ-5, SF-36, and WPAI-GH.

The analyses related to the ACQ-5 endpoint are described in the pooled SAP, but are included in the compliance metrics for completeness.

The target overall compliance for the study is 70%.

Overall eCOA compliance (across all eCOAs and all participants) for the study is calculated as:

 $\frac{\textit{Total number of complete eCOAs across all participants}}{\textit{Total expected number of complete eCOAs across all participants}} \times 100$ 

Expected number of complete eCOAs

$$= \sum_{i=1}^{n} \sum_{j=1}^{c} data \ points \ expected \ for \ eCOA_{j}(participant \ i)$$

where c represents the total number of eCOAs collected and n represents the total number of participants.

For daily diary data this means every day is a data point in the denominator. For visit-based endpoints, each visit is a data point in the denominator. The study-level (overall) compliance metric will be summarized by treatment group and total across treatment groups.

A supplemental overall compliance metric will also be calculated for the study. The supplemental calculation will be based on an interval-based definition for daily diary data that is defined within Section 6.3.4.2 for a four-week interval result to be non-missing in the analysis. The number of data points in the denominator for the interval-based definition becomes the number of four-week time periods that are assessed, including the baseline assessment. Participants are considered compliant for the daily diary endpoints if

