#### **6.3.4.2.** Daily Diary

Participants are to complete a daily diary assessment each morning. Table 2 below displays which daily diary records are included for each analysis time period. Any daily diary data collected post the 52-week time period will not be included in the Weeks 49-52 analysis of diary data.

Table 2 Daily Diary Assessment Windows

Analysis for AM Measures		
Beginning Timepoint (Day)	Ending Timepoint (Day)	Analysis Time Period
-27	1	Baseline
2	29	Weeks 1 – 4
30	57	Weeks 5 – 8
58	85	Weeks 9 – 12
86	113	Week 13 – 16
114	141	Weeks 17 – 20
142	169	Weeks 21 – 24
170	197	Weeks 25 – 28
198	225	Weeks 29 – 32
226	253	Weeks 33 – 36
254	281	Weeks 37 – 40
282	309	Weeks 41 – 44
310	337	Weeks 45 – 48
338	365	Weeks 49 – 52

Note: There is no Day 0 in CDISC reporting. Days -27 to -1 are immediately pre-randomization and Day 1 is the day of randomization (Visit 2). For the baseline time period, all values from Day -27 to Day 1 will be included in the baseline average; however, there must be a minimum of 4 non-missing values from Day -6 to Day 1 inclusive in order to derive the baseline, otherwise it will be set to missing.

Note: For each 4-week post-baseline time period the average will only be derived if there are non-missing values for at least 4 days out of 7 in at least 3 out of 4 weeks, with at least 15 minimum values, otherwise it will be set to missing.

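### The diary baseline rule and the randomisation diary rule are offset by one day, so an eligible participant can be left without a VRS baseline

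*SAP*

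**What the plan says.** Randomisation criterion 3 in Protocol 5.3 asks for "eDiary compliance for at least 4 out of the last 7 days preceding Visit 2 (excluding Visit 2", so the Visit 2 entry does not count towards eligibility. Criterion 2 uses the same seven days for the mean nasal obstruction score.

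SAP 4.1.2 defines the diary baseline as a 28-day average: "This means the average will be based on the non-missing data from Day -27 to Day 1 inclusive". It then adds a condition: "There must be a minimum of 4 non-missing values from Day -6 to Day 1 inclusive". If the condition fails, the baseline is missing. The note to Table 2 in SAP 6.3.4.2 repeats the condition and fixes the calendar: "There is no Day 0 in CDISC reporting", and "Day 1 is the day of randomization (Visit 2". The general rule in SAP 4.1.2 is that "if baseline data is missing no derivation will be performed and baseline will be set to missing". Visit-based endpoints can fall back on an unscheduled or screening measurement. Diary endpoints have no such fallback.

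SAP 4.2.2 analyses change from baseline in an MMRM that includes the baseline score as a covariate. SAP 4.4.1 states that responder status is not derived for a participant without a baseline.

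**The concern.** Both rules ask for 4 diary values in 7 days, but the weeks differ by one day. The SAP window drops Day -7 and adds Day 1. A participant can therefore be randomised on a valid 7-day obstruction mean, be dosed, enter the Full Analysis Set, and then be treated as having no diary baseline.

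This matters because the nasal obstruction VRS is one of two co-primary endpoints and both must succeed. The same baseline rule governs three of the six within-study secondary endpoints (rhinorrhoea, loss of smell, and nasal obstruction at Weeks 21 to 24). It also governs facial pain, mucus in throat, the VRS composites and the overall VAS. Losing randomised participants through an offset between two counting rules is hard to defend afterwards.

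**Working it through.** **1. The plan's own figure.** SAP 5 and Protocol 9.5 give a VRS difference of 0.70, SD 0.84, two-sided 5%, 125 randomised per arm and a 5% non-evaluable allowance.
- 125 × 0.95 = 118.75, consistent with the stated minimum of 118 per arm.
- Standard error = 0.84 × √(2/118) = 0.1094.
- Smallest significant difference = 1.96 × 0.1094 = 0.214. The plan says 0.21.
- Power = Φ(0.70/0.1094 − 1.96) = Φ(4.44) = 0.999996. The plan says above 99%.

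The stated figures reproduce.

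**2. The two windows.** With no Day 0 and Visit 2 on Day 1:
- Eligibility: Days -7, -6, -5, -4, -3, -2, -1.
- Baseline condition: Days -6, -5, -4, -3, -2, -1, 1.

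They share six days.

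**3. Who is caught.** There are 2⁸ = 256 entry/no-entry patterns over these eight days, and 128 meet the eligibility rule. Of those, C(6,3) = 20 fail the baseline condition. All 20 have the same form: an entry on Day -7, exactly 3 entries in Day -6 to Day -1, and none on Day 1. An example is entries on Days -7, -3, -2 and -1 only. If the baseline condition used the eligibility days, none of the 128 would fail. (20 of 128 counts patterns; it is not a probability.)

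**4. What follows for that participant.** With no baseline there is no change score, and a model covariate is missing. The participant therefore contributes nothing to the VRS MMRM. The SAP does not say this in words; it follows from 4.1.2 and 4.2.2. The imputation analysis in SAP 4.2.3 uses the same covariates, so it offers no stated rescue.

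**5. How often.** Let p be daily completion in the run-in and q completion on Day 1. Both are assumed, with days independent:

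P(lost | eligible) = p × C(6,3) p³(1−p)³ × (1−q) / P(Bin(7,p) ≥ 4)

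At p = 0.70 and q = 0.90 this is 0.70 × 20 × 0.343 × 0.027 × 0.10 / 0.874 = 0.0148.

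| p | q | Loss | Of 250 |
|---|---|---|---|
| 70% | 100% | 0 | 0 |
| 70% | 98% | 0.3% | 0.7 |
| 70% | 95% | 0.7% | 1.9 |
| 70% | 90% | 1.5% | 3.7 |
| 70% | 70% | 4.5% | 11.1 |
| 80% | 95% | 0.3% | 0.8 |
| 80% | 80% | 1.4% | 3.4 |
| 90% | 90% | 0.13% | 0.3 |

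**6. Effect on power.** With 104 per arm instead of 118, VRS power is still above 0.9999. It falls below 99% only at about 52 per arm.

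**The case against.** The SAP condition is coherent taken alone. It covers the last seven days of the 28-day baseline window, and 4 of 7 is also the weekly threshold used after baseline. A participant who fails it has only 3 values in that week and has missed the Visit 2 entry, so the data do fall short of a pre-specified minimum. That stands. The criticism is only that this minimum differs by a day from the one used to admit the participant.

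A missed Day 1 entry is also unlikely. In the Protocol 1.3 schedule, Visit 2 is in-clinic, the VRS is marked there, an eDiary compliance check takes place, and questionnaires come before other assessments. That stands too, and it is why the rows with high q are the realistic ones. It does not remove the gap, because a Day 1 entry is not a condition of randomisation.

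A reader might go further and put the 70% target from SAP 6.2.1 on every day including Day 1. That gives 4.5%, or 11 of 250, which looks like nearly the whole 5% non-evaluable allowance. The documents do not support this. The 70% is a target across all electronic assessments from baseline to study end, not a run-in rate, a Day 1 rate or a forecast.

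A reader might also infer a threat to power or a biased comparison. Step 6 rules out the first. On the second, the loss depends only on diary entries up to the morning of Day 1, before treatment can act, so it is not related to treatment.

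**Conclusion.** The one-day offset is present in the current protocol and SAP, and it can remove an eligible, dosed participant from a co-primary analysis. It is a minor point. The expected loss is about 1 to 4 of 250 at 70% daily completion with 90% to 98% on Day 1, about 1 of 250 at 80% daily with 95% on Day 1, and none if Day 1 is always completed. The 4.5% figure belongs only to the extreme case of 70% on every day including Day 1.

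These sizes rest on assumed completion rates, independence between days, and a compliant diary day supplying a VRS value. Exclusion from the MMRM is inferred; non-derivation of responder status is explicit. The objection to the rule is the avoidable exclusion after randomisation, not lost power or bias.

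**What to change.** In SAP 4.1.2 and the note to Table 2 in SAP 6.3.4.2, derive the diary baseline if at least 4 non-missing values exist in Day -7 to Day -1 **or** in Day -6 to Day 1. Keep the Day -27 to Day 1 average as the baseline value.

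Every participant who meets randomisation criterion 3 then has a diary baseline. Because the second window is retained, nobody who has a baseline under the current rule loses it. The cost is one sentence in each of two places, with no new data and no change to the model or sample size. It should be made before unblinding.

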#### 4.1.3. Multicenter Studies

For the purposes of covariate adjustment in the statistical analysis, countries will be grouped into the following 3 regions: Europe (EU); United States (US); Rest of World (RoW). The countries that form these regions will include:

- Europe (EU): Poland; Romania; Spain; Sweden; Italy
- United States (US): United States
- Rest of World (RoW): China; Japan; Turkey

If there are insufficient subjects in each region for the statistical procedures to converge satisfactorily, the combining of regions will be considered.

### 4.2. Primary Endpoints Analyses

### 4.2.1. Definition of endpoints

The co-primary endpoints are:

- a) Change from baseline in total endoscopic NP score at Week 52 (centrally read)
- b) Change from baseline in mean nasal obstruction score (verbal response scale [VRS]) from Week 49 through to Week 52

The total endoscopic NP score is assessed in the clinic at visits 2, 5, 7, 9, 11, 13, 15 and 16, or early withdrawal visit (weeks 0, 12, 20, 26, 32, 40, 48 and 52). The score is then graded by independent reviewers at a central lab who are blinded to treatment. The total score is reported as the sum of the right and left nostril scores and ranges from 0 to 8, with higher scores indicating greater disease severity. Non-missing scores must be available for both sides for the combined score to be calculated; otherwise the score will be set to a value of 9 to indicate a missing or unreadable value.

The nasal obstruction VRS score will be collected daily in the morning via the eDiary. Each day the participant will indicate the severity of their symptoms giving a score ranging from 0 to 3, with the 4 options indicating no symptoms, mild symptoms, moderate symptoms, and severe symptoms. The daily data will be collapsed into thirteen 4-week time periods, with the value for each time period based on the average of the non-missing days covered by that time period as described in Section 6.3.4.2. For each 4-week time period the average will only be derived if there are non-missing values for at least 4 days out of 7 in at least 3 out of 4 weeks, with at least 15 minimum values, otherwise it will be set to missing.

As described in Section 1.1.2, under the primary estimand, the intercurrent events of (i) surgery and (ii) initiation of a disease-modulating medication for CRSwNP, will be handled using a composite strategy by incorporating occurrence of the event into the definition of the endpoint. Specifically, participants who experience the intercurrent event will be assigned the worst possible value of the relevant score for all assessments following the intercurrent event (i.e. the worst value that it is possible to select on the given scale). This means that a participant who experiences the intercurrent event will be assigned a total endoscopic NP score of 8 for every scheduled clinic visit after the date of the first intercurrent intercurrent event (regardless of whether the visit occurred) and a nasal obstruction VRS score of 3 for every day after the date of the first intercurrent event. All other intercurrent events described under the primary estimand strategy in Section 1.1.2 will be handled using a treatment policy strategy.

The study is designed to continue collecting data for participants who have prematurely discontinued from randomized treatment and off-treatment data collected for these participants will be included in the analysis. Missing data will be assumed to be missing at random (MAR). Summary statistics will be produced for each visit/4-week time-period by treatment group for the co-primary endpoints.

### 4.2.2. Main analytical approach

#### **Model Specification**

Statistical analyses will be performed using a Mixed Models Repeated Measures (MMRM) model with covariates of treatment group, baseline score, log(e) baseline blood eosinophil count, region, previous surgery for nasal polyps, visit and interaction terms for visit by baseline score and visit by treatment group.

### Model Checking & Diagnostics

- The Kenward-Roger (KR) method [Kenward, 1997] for approximating the denominator degrees of freedom and correcting for bias in the estimated variance-covariance of the fixed effects will be used in the analyses. This will be achieved by specifying the DDFM=KR option in the MODEL statement within PROC MIXED.
- For mixed model repeated measures (MMRM) models, an unstructured covariance structure for the R matrix will be used by specifying 'TYPE=UN' in the REPEATED statement.
  - In the event that the model fails to converge, model simplification methods will be considered (e.g., adjusting covariate structure, streamlining timepoints)

Appropriate graphs will be reviewed as part of the model checking process to ensure that
distributional assumptions hold. These will include a normal probability plot of the residuals
and a plot of the residuals versus the fitted values (checking the normality assumption and
constant variance assumption of the model, respectively).

#### Model Results Presentation

- For each visit / time-period, the adjusted mean change from baseline with corresponding standard error for each treatment group will be presented. The estimated treatment difference will be presented together with 95% confidence interval (CI) for the difference and p-value for the inequality comparison.
- The adjusted mean change from baseline for each treatment, with corresponding 95% CIs will also be presented graphically across the visits / time-periods.
- A cumulative distribution function (CDF) plot will also be provided for the change from baseline by treatment group

### **Additional Analysis**

- The same primary endpoint analysis will be performed using FAS-Modified analysis set
- The same analyses will be performed with the intercurrent event strategy described under the supplementary estimand.

### 4.2.3. Sensitivity analyses

A missing data sensitivity analyses using multiple imputation (MI) methods will be conducted for each of the co-primary endpoints to investigate the impact of missing data and to examine the robustness of the analyses of the primary endpoints to departures from the assumption that missing data are MAR. These analyses will use the same estimand strategy as outlined for the co-primary endpoints in Section 1.1.2. The MI methods are based on pattern-mixture models described by Carpenter [Carpenter, 2013]. The pattern-mixture model approach to sensitivity analysis models the distribution of a response as the mixture of a distribution of the observed responses and a distribution of the missing responses.

### Sensitivity Analysis 1

For the first sensitivity analysis, participants with missing data at Week 52 who had taken their Week 26 dose of interventional product (and are therefore considered on-treatment at Week 52) will have missing data imputed under the assumption of MAR. Participants with missing data at Week 52 who had not taken their Week 26 dose of interventional product (and are therefore considered off-treatment at Week 52) will have their monotone missing data (i.e. after their final non-missing time point) imputed using a jump to reference (J2R) approach. Implementation of the J2R method assumes that for participants in the experimental treatment group (Depemokimab) with missing data, their imputed mean response is that of the reference treatment group (Placebo).

Multivariate normal models will be fitted using a Markov Chain Monte Carlo (MCMC) approach. The covariates will be the same as for the primary analysis. The independent samples drawn from the posterior distributions for the mean and variance-covariance matrix provide input into the imputation model. For each participant with missing data, these sampled values of the parameters for mean vectors and the variance-covariance

matrices specify a joint distribution for their observed and unobserved outcome data. Under the J2R approach, the mean estimate is constructed using the estimated beta associated with the reference treatment, as well as the participant's other covariates.

For each participant with missing data, this joint pattern-specific distribution can be used to construct the conditional distribution of their missing data given their observed data. The missing data is sampled once from this distribution to create a single dataset for each imputation. Together these form a series of complete imputed datasets for each of the primary endpoints (with imputed data under either MAR or J2R).

Each imputation dataset will be analyzed using the same methodology as for the primary analysis and the results from each analysis of each sample will then be combined using Rubin's method [Rubin, 1987] as implemented in PROC MIANALYZE in SAS.

Results presentation will be the same for the co-primary analyses described in Section 4.2.2 for the EOS visit / time period. Additionally, for each of the co-primary endpoints, for the EOS visit / time-period only, a forest plot will be produced to present the estimated treatment differences and 95% CIs for the primary estimand using FAS, the supplementary estimand using FAS, the primary estimand using FAS-Modified, and the J2R approach.

#### Sensitivity Analysis 2

An additional tipping point sensitivity analysis will explore the impact of missing data by using differing assumptions regarding the endoscopic NP score at Week 52 and the nasal obstruction VRS at Weeks 49-52 in subjects who withdraw from the study. Subjects who withdrew from study early will have missing data imputed for the period of time between withdrawal from the study to the Week 52 visit / Week 49 – 52 time period based on a range of values for the mean NP score / mean nasal obstruction VRS following study withdrawal. Assumptions about missing values on the treatment arm and placebo arm will vary independently, and will include scenarios where participants with missing data in the active arm have worse outcomes than participants with missing data in the placebo arm. This analysis will allow for determination of 'tipping point(s)' of the values for missing data that would cause a change in the statistical significance of the result of the treatment comparison.

As a first step, participants with missing data will have missing data imputed under the assumption of MAR. For each treatment group, the imputed values will vary separately by a value of delta, where delta represents a change in endoscopic NP score / mean nasal obstruction VRS over a 4-week interval. The deltas investigated will cover a range that is plausible for the respective endpoint under the MAR assumption. For NP score, the deltas evaluated will range from -8 to 8 by 0.5 increments. For nasal obstruction VRS, the deltas evaluated will range from -1.5 to 1.5 in 0.25 increments. The final range and increment of deltas will be investigated on final data and may be adjusted to ensure it supports a meaningful tipping point range.

The tipping point multiple imputation method will be based on pattern mixture models [Keene, 2014]. Each imputation dataset will be analyzed using the same methodology as for the primary analysis and the results from each analysis of each sample will then be combined using Rubin's method [Rubin, 1987] as implemented in PROC MIANALYZE in SAS.

A table of p-values for each treatment comparison made across the range of imputed values (deltas) for each respective endpoint will be presented. Graphics depicting treatment difference and non-significant vs. significant surfaces will be produced for the range of imputed values (deltas) for each respective endpoint.

The seeds for all planned MI sensitivity analyses will be '218079'.

